Secondary Aim: As a secondary aim we will examine effect sizes for PPPA versus the standard PA intervention on putative mediators that may underlie the efficacy of PPPA in improving PA outcomes, including positive and negative affect, optimism, happiness, life satisfaction, social support for PA, and PA enjoyment. Putative mediators will be assessed at mid-treatment (week 3), immediate post-treatment, and follow-ups. The proposed research will set the stage for a randomized clinical trial, which would be powered to test main effects and mediational mechanisms of action. Ultimately, we expect this program of research will result in a well-specified, efficacious PA promotion intervention that could be readily disseminated.

A. SIGNIFICANCE

A.1. Health benefits of physical activity for cancer prevention. The benefits of physical activity (PA) for cancer prevention are significant. Numerous large cohort studies and systematic reviews have shown consistent evidence of an inverse relationship between engagement in PA and risk of breast and colon cancers,³⁻¹⁷ with some evidence for endometrial,^{18,19} pancreatic,²⁰ and lung^{21,22} cancers. Moreover, a recent pooled-cohort study of 1.44 million adults showed associations between leisure-time PA and 13 cancer types.¹ As a result of the large and growing evidence base showing the protective effects of PA, NCI has emphasized funding for research on the development of PA promotion interventions to reduce risk of multiple cancers.²

A.2. Low rates of PA among overweight adults. Despite the many health benefits of PA, rates of regular PA are low, particularly among overweight and obese adults. Studies based on accelerometer data show that less than 5% of overweight and obese adults meet national guidelines of expending 500-1000 MET-minutes (intensity in metabolic equivalents times minutes) per week through PA.³⁵ Moreover, overweight adults spend less time in moderate-to-vigorous PA than normal weight adults,³⁵⁻³⁹ and PA promotion studies have shown that overweight adults are more likely to discontinue PA programs and discontinue them sooner.^{40,41} Thus, there is an urgent need to improve adherence to PA programs among low-active overweight and obese adults.

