C.2.c. Orientation, baseline assessment, and YMCA membership. Individuals who are eligible on an initial phone screen will be asked to attend an orientation session at the local YMCA where the Research Assistant (RA) will provide more information about the study, and the opportunity to ask questions prior to signing

consent. After orientation and consent, the RA will obtain height and weight, and observe participants use of YMCA aerobic exercise equipment to ensure adequate capacity for moderate intensity PA. Participants who remain eligible following baseline assessments will take with them an accelerometer to assess baseline frequency, duration, and intensity of **moderate-to-vigorous PA (MVPA)** over a one-week period. Orientations will be group-based and ongoing until 15 participants are eligible, thus allowing for a minimum of 10 participants in the PPPA intervention group. We expect to achieve this number within 2-3 weeks of recruitment.

Participants will be provided a 3-month YMCA membership upon arrival at session 1 of the PPPA intervention.

C.2.d. Primary treatment components. There will be 6 weekly one-hour PPPA treatment sessions consisting of core PA promotion content and positive psychology content. All participants will receive a treatment binder that contains information about each session. **Core PA promotion content** will be based on our previous PA promotion studies, and will focus on (a) health benefits of PA, (b) individualized PA intensity prescriptions based on age and resting heart rate, and instruction on how to gauge PA intensity, (c) goal-setting and self-monitoring, and (d) tips on overcoming barriers to PA, including time-management. Participants will be instructed to target 30-60 min/day 5 days/week of MVPA consistent with national guidelines.⁹⁶ PA content will be concentrated in sessions 1 and 2, but content on goal-setting, self-monitoring, and overcoming barriers will continue throughout the 6-week period. **Positive psychology content:** The exercises listed below begin in session 1 and will continue throughout the 6-week program, with PPPA homework completed via text-messaging. Specific content for each session will be determined upon development of the intervention manual.

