C.2.h. Measures. Demographics will be collected at baseline, including gender, ethnicity/race, education, marital/relationship status, income, and employment. **PA outcomes:** Total volume of MVPA (i.e., min of MVPA weighted by intensity) expressed in MET minutes will be determined by accelerometers (Actigraph wGT3x-BT) worn during one-week periods at baseline (prior to the start of treatment), immediate post-treatment, and 3-month follow-up. Accelerometers will be worn on the right hip at the anterior axillary line using an elastic belt, consistent with standard practices.¹⁰⁰ Instructions, including proper positioning, will be provided in person at baseline and again at the final, week 6, PPPA session. As our team has done in previous studies,^{101,102} we will use ActiLife software to determine PA intensity.¹⁰³ However, we will also be collecting raw accelerometry output data thus allowing for consideration of alternative cutpoints (e.g.¹⁰⁴⁻¹⁰⁶) and/or data processing approaches (i.e., pattern recognition¹⁰⁷) as the literature develops. MVPA will also be self-reported in diary form over the 7-day accelerometer period. This procedure is standard in the field, as it helps to verify accelerometry outputs and also accounts for MVPA that is not easily recorded by the accelerometer (e.g., stationary bicycle).

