Intervention feasibility and acceptability: We will record PPPA session attendance and responses to the evening text-messages as objective indices of feasibility and acceptability. Retention will be coded as a dichotomous variable with participants who complete the sixth and final treatment session characterized as treatment "completers" and those not attending the final session as "non-completers." Participants will complete a Treatment Strategies Questionnaire at sessions 2-6, which will assess frequency of use of specific PPPA strategies in the past week such as planning opportunities for PA and completing the 3 Good Things exercise.¹⁰⁸ Responses to the questions will be used to inform the treatment feedback process. Satisfaction will also be assessed with the Client Satisfaction Questionnaire, an 8-item questionnaire that will be administered at the 7-week follow-up to assess participant satisfaction with provided services (CSQ-8).¹⁰⁹ **Positive psychology measures and putative mediators:** The Values in Action Survey⁹⁷ will be administered to all participants at baseline, and participants will receive feedback on their 5 "Signature Strengths" derived from this measure.^{81,82} The following putative mediators will be assessed at mid-treatment (session 3), post-treatment (week 7), and 13-week follow-ups. Short-term changes in positive and negative affect will be assessed with the Positive and Negative Affect Scale.¹¹⁰ Trait optimism will be assessed with the well-validated revised Life Orientation Scale.¹¹¹ Subjective happiness and subjective well-being will be assessed with the 4-item Subjective Happiness Scale¹¹² and the 5-item Satisfaction with Life Scale.¹¹³ Social support will be assessed at baseline and follow-ups using the 13-item Social Support for Exercise Scale.¹¹⁴ Finally, PA enjoyment will be assessed with the 18-item Physical Activity Enjoyment Scale.¹¹⁵

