C.2.i. Intervention refinement. During the initial PPPA intervention group, the intervention manual and materials will be refined based on an iterative treatment development process. After each of the sessions is completed, participants will complete brief questionnaires on perceived session utility and their use of PPPA strategies in the past week. Open-ended questions will also assess the utility and acceptability of the treatment sessions and exercises. Intervention refinement will also be based on investigators' weekly reviews and discussion of the audio-recorded sessions. This will lead to a revised PPPA manual going into Phase 2.

C.3. Additional procedures for Aim 2: Preliminary testing (ORBIT phase 2).

Procedures for Aim 2 will be the same as Aim 1, with the following exceptions:

C.3.a. Recruitment, enrollment, and randomization. We will recruit 60 participants who will be randomized at a 2:1 ratio to PPPA treatment versus **standard PA promotion (SPA)** in order to focus resources on the PPPA program while still including a comparison for preliminary testing. We will run 4 groups of PPPA and 2 groups of SPA, with 10 participants per group. Urn randomization will be used to balance on sex and BMI.

C.3.b. PPPA condition. The PPPA condition will follow the revised treatment manual and text messaging program, based on feedback from Aim 1, but will follow the basic themes and procedures noted above.

C.3.c. SPA condition. The SPA condition will consist of the **core PA promotion content** (see above). To equate for session duration, additional information on health and wellness will be delivered by the staff, including topics such as skin care, alcohol use, and heart health. **Text messages** for the SPA condition will consist of reminders to engage in PA and other general motivational messages, thus controlling for total number of text messages. Because all of the PA-related content in the SPA condition will also be provided in the PPPA condition, this is essentially *an additive design, with an equal contact control*.

C.3.d. Additional 6-month follow-up and 6-month YMCA membership. For both conditions, YMCA memberships will be extended for 6 months, and an additional assessment will take place at month 6 (wk 26).

C.4. Participant retention, compliance, and incentives

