Aim 2. We will focus on determining **effect sizes** for PPPA rather than strict statistical significance testing. At the same time, we are well aware of the dangers of relying exclusively on small-scale pilots to determine the promise of novel treatment approaches,¹¹⁹ as estimates from small samples tend to have large standard errors. Thus our hope is that we find a pattern of results that is supportive of the experimental treatment. Similar PPIs have shown medium to large effect sizes on depressive symptoms, positive affect, and happiness. Effect size estimates will include Cohen's *d* (for unadjusted between-group comparisons) and f^2 (for longitudinal multivariate models of treatment effect). For the purpose of estimating the effects of treatment on both MVPA and the putative mediators, we will fit a series of mixed effects regression models in which, for example, min/week of objectively measured MVPA at post treatment, and at 13 and 26 weeks will be simultaneously regressed on treatment group, baseline MVPA and variables not balanced by randomization. Models will allow for estimating both effects of treatment on MVPA post treatment, as well as maintenance of MVPA from 7 weeks through 6m. A similar strategy will be used to estimate effect sizes with respect to treatment effects on the putative mediators. We believe a sample size of 60 (40 intervention versus 20 control) should allow adequate examination of PPPA intervention effect sizes while staying within the scope of a developmental project. We recognize that only medium to large effect sizes will be likely to attain statistical significance with an unbalanced sample of this size. **Feasibility and acceptability:** Between-group differences for continuous measures (number of sessions attended and client satisfaction scores at post-treatment) will be conducted using analysis of variance and chi-squared analyses for dichotomous variables (treatment retention). We anticipate that treatment attendance and completion will either be equal or will be higher in the PPPA condition.

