SPA condition. The SPA condition will consist of the **core PA promotion content** (see above). To equate for session duration, additional information on health and wellness will be delivered by the staff, including topics such as skin care, alcohol use, and heart health. **Text messages** for the SPA condition will consist of reminders to engage in PA and other general motivational messages, thus controlling for total number of text messages. Because all of the PA-related content in the SPA condition will also be provided in the PPPA condition, this is essentially an additive design, with an equal contact control.

Additional 6-month follow-up and 6-month YMCA membership. For both conditions, YMCA memberships will be extended for 6 months, and an additional assessment will take place at month 6 (wk 26).

Participant retention, compliance, and incentives

We expect from our prior research experience to be able to contact 85-95% of participants at each follow-up assessment.^{108,116,117} We will employ our previously successful procedures to maintain high follow-up rates.^{108,116-118} Additionally, participants will be paid \$25 for 7-week follow up, \$25 for the 13-week follow up, and (in Study 2) \$25 for the 26-week follow up. These payments are not contingent upon PA level.

1.b. Sources of Materials.

Telephone interview: Screening for eligibility criteria at baseline.

Questionnaires: Measuring demographics, and putative mediators of treatment effects at baseline, mid-treatment, post-treatment, and 13 week (3 month) and (for Study 2) 26 week (6 month) follow-ups.

Weekly questionnaires: Weekly questionnaires during the treatment period will assess frequency of use of specific PPPA strategies.

Accelerometers and physical activity diaries: For assessment of PA behavior at baseline, post-treatment, and 13 week (3 month) and (for Study 2) 26 week (6 month) follow-ups.

Text messages: Participant responses to open-ended text messages regarding intervention exercises (i.e., homework) for both assessment and treatment planning purposes.

1.c. Potential Risks.

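### The Aim 2 models leave their covariates open, so the urn factors sex and BMI may or may not be adjusted for; naming both is a minor and nearly free improvement.

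*Combined protocol and SAP*

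**What the plan says.** C.5, under Aim 2, describes mixed models in which weekly activity minutes at post-treatment, 13 weeks and 26 weeks "will be simultaneously regressed on treatment group, baseline MVPA and variables not balanced by randomization". The mediators are to be handled in a similar way. No section lists the extra covariates or gives a test or threshold for calling a variable unbalanced.

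C.3.a says "Urn randomization will be used to balance on sex and BMI", with 60 participants allocated 2:1. Neither factor is named as a covariate. The only other covariate mentioned is smoking status, and that is for a future trial (C.2.b).

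C.5 gives Cohen's d for unadjusted comparisons and "f^2 (for longitudinal multivariate models of treatment effect") for the models, and puts effect sizes ahead of significance tests.

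The data for both factors are already collected: demographics "including gender, ethnicity/race, education, marital/relationship status, income, and employment" (C.2.h), and at orientation "the RA will obtain height and weight" (C.2.c).

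**The concern.** The phrase can be read in two ways. If it means variables on which the urn does not balance, sex and BMI are always excluded. If it means variables found to differ between arms, sex and BMI enter only when some unstated criterion is met. Neither reading guarantees that the analysis follows the factors used to randomise, and two analysts following C.5 faithfully could fit different models.

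Two things are at stake. The first is a little precision: if sex and BMI are prognostic and left out, the standard error is slightly too large. The second is the reported effect size. f² depends on residual variance and so on the covariates in the model, which means that one treatment effect can give different f² values. C.5 makes effect sizes the main product of this pilot.

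**Working it through.** **Inputs from the documents.** n = 60, 40 PPPA versus 20 control (4 groups of 10 and 2 groups of 10); 2:1 urn on sex and BMI; BMI 25-40; 85-95% contacted at each follow-up (C.4). The plan gives no power calculation, alpha, SD or target effect.

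**Consistency check.** At two-sided 0.05 (assumed), the smallest observed d that reaches significance is t(0.975, 58) × √(1/40 + 1/20) = 2.00 × 0.274 = 0.55. Power is 43% at d = 0.5 and 82% at d = 0.8. This agrees with the plan's remark that only effects of at least medium size are likely to be significant.

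**Assumptions.** R² is the share of outcome variance, after the baseline value, explained by sex and BMI together; 0 to 0.20 is shown. The BMI and activity limits on entry make the low end more plausible. The urn details are not given, so 16 settings were simulated: marginal or crossed urns, 2 or 3 BMI levels, starting balls 2:1 or 10:5, 50% or 70% women, and BMI uniform on 25-40. Each setting had 6,000 trials (3,000 for the p < 0.05 imbalance test). The single-visit model is least squares on arm and baseline, with or without sex and continuous BMI. The three-visit model has a random intercept, within-person correlation 0.5 or 0.7 and 10% missing per visit (1,500 trials in each of 3 settings); there R² is a share of between-person variance.

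**f².** For an effect of d residual SDs at 2:1, f² = d² × (2/3)(1/3)/(1 − R²). With d = 0.5, the value without both factors is 0.25 × 0.2222 = 0.056. With both, it is divided by 0.95, 0.90 or 0.80.

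**Ratios, with both factors to without:**

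| R² | Model SE, one visit | True SD, one visit | Model SE, three visits | True SD, three visits | f² with both |
|---|---|---|---|---|---|
| 0 | 1.008-1.012 | 1.006-1.013 | 1.010-1.011 | 1.005-1.012 | 0.056 |
| 0.05 | 0.982-0.986 | 0.989-1.000 | 0.988-0.993 | 0.995-1.002 | 0.058 (+5%) |
| 0.10 | 0.956-0.960 | 0.970-0.985 | 0.966-0.973 | 0.981-0.990 | 0.062 (+11%) |
| 0.20 | 0.900-0.905 | 0.931-0.953 | 0.919-0.934 | 0.951-0.964 | 0.069 (+25%) |

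The one-visit model SE follows √(1 − R²) × 1.01; at R² = 0.10, 0.949 × 1.01 = 0.958. The true SD falls by less because the urn has already removed part of the chance imbalance. Much of the fall in the model SE is therefore corrected conservatism, not a more precise estimate. The simulated mean f² ratios (one visit, 4,000 trials) were 1.02, 1.06, 1.11 and 1.22.

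**Test size without both factors** (nominal 5%): 4.7-5.6%, 4.4-5.5%, 4.1-5.0% and 3.6-4.4% at the four R² values. There is no inflation beyond simulation error.

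**How often sex or BMI would count as unbalanced** (assumed criteria): 0.7-3.4% of trials at p < 0.05, 51-63% at a standardised difference above 0.2, and 86-91% above 0.1.

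**Cost in degrees of freedom.** Residual df go from 57 to 55. The d detectable with 80% power moves from 0.7805 to 0.7810 at 40 versus 20, and from 0.849 to 0.850 at 85% follow-up (34 versus 17).

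**The open choice itself.** With eight candidate covariates, selecting mechanically at p < 0.10 or at a standardised difference above 0.25 kept test size at 3.9-4.9%. In a worst case, free choice among all 256 subsets of eight non-prognostic covariates rejected a true null in about 9% of 600 runs (Monte Carlo SE about 1.2 points). The median spread in the estimated effect across subsets was about 0.19 SD. This is an upper bound, not a prediction.

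**The case against.** The strongest reply is that the effect is negligible. At the more plausible R² of 0 to 0.05, the true SD changes by +1% to -1%, and at R² = 0 the change is pure cost. The f² shift of 0.002 at R² = 0.05 is lost in sampling noise: simulating f² for a 0.5 SD effect at 40 versus 20 gives a mean of 0.079, with 2.5 and 97.5 percentiles of 0.0005 and 0.27. The f² figures are for a single visit, whereas the plan uses f² for longitudinal models. The flag rates rest on assumed urns and thresholds. Finding variables unbalanced is also the more natural reading, and this is a pilot that sets significance testing aside.

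All of this stands as a limit on size, and it is why the point is minor. It does not remove the gap. On the natural reading the threshold is still missing, and the flag rates serve only to show how strongly the model depends on it; they do not predict this trial.

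A second reply is that an unstated rule cannot be certified as free of bias. That is right. Selection on baseline imbalance uses no outcome data and is harmless only if a criterion is fixed and applied mechanically. The larger exposure is the open choice among other baseline variables. This strengthens the case for a closed covariate list.

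**Conclusion.** The concern holds and is minor. The text leaves the covariates open, and this part of the finding needs no assumption. Omitting sex and BMI is at worst slightly conservative. Naming them costs about 1% in SE if neither is prognostic. If they explain 10% or 20% of residual variance, the one-visit true SD falls by about 1.5-3% or 5-7%. The sizes depend on the assumed R², urn settings and imbalance criteria. The six delivery groups are not modelled; group-level variance would make the relative gain smaller. The change is worth making because it costs so little and settles in advance which model is fitted.

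**What to change.** In C.5, replace the open phrase with a closed list for every activity and mediator model: arm, the baseline value of that outcome, sex and BMI. State in advance whether BMI is continuous or in the form used in the urn. Say that no other covariates enter the main model. Keep adjustment for observed imbalance only as a labelled sensitivity analysis with its criterion written down, and report each f² with the covariates of its model.

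For the activity models this is one sentence and two degrees of freedom (with continuous or two-level BMI), using data the urn already requires.

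The mediator models need one step first. Section 1.b (Sources of Materials) has questionnaires "Measuring demographics, and putative mediators of treatment effects at baseline, mid-treatment, post-treatment" and later, so it includes baseline. The Secondary Aim says "Putative mediators will be assessed at mid-treatment (week 3), immediate post-treatment, and follow-ups", and C.2.h says "The following putative mediators will be assessed at mid-treatment (session 3), post-treatment (week 7), and 13-week follow-ups"; neither lists baseline. C.2.h and its repeat in section 1.a list baseline only for social support. These must be reconciled so that each mediator has a baseline value to adjust for.

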Aim 1: Intervention development and refinement (ORBIT Phase 1): The first aim of the project is to translate positive psychology theory and research into a 6-week, group-based positive psychology for PA promotion (PPPA) intervention for low-active overweight or obese adults, delivered at local YMCAs, and supplemented with text messaging. The in-person session and text-messaging protocol will be based on the team's previous and ongoing work developing and implementing positive psychology and smoking cessation interventions ([name], [name]), as well as our expertise in exercise promotion interventions ([name]; [name]). We will deliver the intervention prototype among a cohort of 10 low-active (< 60 min/week of structured PA) overweight or obese adults (≥ 18 years; BMI 25-40). Participants and clinician-investigators will provide ongoing feedback regarding their experiences with application of the intervention in an iterative development process to refine the protocol, improve the utility of the intervention and modify intervention materials. The milestone for Phase 1 is a finalized PPPA intervention protocol by month 6 of year 1.

Aim 2: Preliminary testing (ORBIT Phase 2): The second aim of the project is to test proof-of-concept and feasibility of PPPA. This will be accomplished in the context of a randomized pilot study among 60 low-active overweight or obese adults at local YMCAs. In an additive design, participants will be randomized in a 2:1 ratio to PPPA versus a control intervention including only the standard PA promotion components of the PPPA intervention (i.e., PA education, self-monitoring, and goal-setting), with equal frequency of staff contact and text message delivery. All participants will be followed for 6 months, including the 6-week treatment period, and will receive a 6-month YMCA membership to equate access to PA facilities. We hypothesize that participants in PPPA, relative to the standard PA intervention will: demonstrate equal or greater session treatment retention and satisfaction (H1); and more min per week of PA as measured by accelerometry at immediate post-treatment (week 7) and weeks 13 and week 26 (H2).

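### With 40 v 20 participants, ANOVA on two capped scores would overstate the precision of the H1 differences if PPPA does better near the ceiling; a Welch comparison avoids this (minor).

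*Combined protocol and SAP*

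**What the plan says.** In the combined protocol and SAP, section C.5 (Data analysis, Aim 2, under Feasibility and acceptability) sets the method for the two continuous H1 measures: "number of sessions attended and client satisfaction scores at post-treatment) will be conducted using analysis of variance". Treatment retention, being dichotomous, goes to a chi-squared test and is not at issue here. No unequal-variance, rank, robust or bootstrap version is named, and no interval method or alpha is given for these measures.

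The allocation is unequal. Section C.3.a plans "We will run 4 groups of PPPA and 2 groups of SPA, with 10 participants per group", and C.5 gives the split as "40 intervention versus 20 control".

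Both scores are bounded. On attendance, C.2.d says "There will be 6 weekly one-hour PPPA treatment sessions"; C.3 carries the Aim 1 procedures over to Aim 2 and describes SPA as an equal-contact control, so the cap of six applies to both arms. Satisfaction is the CSQ-8, described in C.2.h as "an 8-item questionnaire that will be administered at the 7-week follow-up".

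On direction, C.5 states: "We anticipate that treatment attendance and completion will either be equal or will be higher in the PPPA condition". That sentence does not mention satisfaction. H1 under Aim 2 does, and it too allows equality: "demonstrate equal or greater session treatment retention and satisfaction (H1").

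**The concern.** ANOVA on two groups estimates one common variance. With equal arms, unequal spreads do no harm to the standard error of the difference. With 40 v 20, the common variance is estimated mainly from PPPA, which supplies 39 of the 58 degrees of freedom, while the uncertainty of the difference comes mainly from the 20 SPA participants. If SPA is the more variable arm, the pooled standard error is too small.

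A ceiling can produce that pattern. As an arm's mean approaches the cap, its scores bunch and its variance shrinks. If PPPA is better attended or better liked and both arms are already in the upper range, the larger arm becomes the less variable one. The intervals around the H1 differences would then be too narrow. These differences are part of what the pilot hands on to the planned larger trial, so their stated precision should be right.

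**Working it through.** **Plan's own figure.** 4 × 10 = 40 PPPA and 2 × 10 = 20 SPA, total 60, as stated.

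**Inputs from the documents.** n = 40 and 20 (C.3.a, C.5); attendance 0 to 6 (C.2.d); CSQ-8 has 8 items (C.2.h).

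**Assumptions, because the documents are silent.** Mean attendance by arm; binomial attendance, or an overdispersed (beta-binomial) version with the same within-person correlation of 0.4 in both arms; a CSQ-8 range of 8 to 32, modelled as a rounded normal score with SD 5, cut off at those limits; two-sided 95% intervals.

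**Step 1: effect of the split.**
- Pooled variance: Sp² = (39·s_P² + 19·s_S²)/58
- Pooled SE = √[Sp²(1/40 + 1/20)] = √(0.075·Sp²)
- True SE = √(s_P²/40 + s_S²/20)

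Pooled SE divided by true SE, by the ratio of SPA SD to PPPA SD:

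| SD ratio | 40 v 20 | 30 v 30 |
|---|---|---|
| 0.8 | 1.08 | 1.00 |
| 1.0 | 1.00 | 1.00 |
| 1.25 | 0.93 | 1.00 |
| 1.5 | 0.88 | 1.00 |
| 2.0 | 0.81 | 1.00 |

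The error needs the 2:1 split; with equal arms it disappears.

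**Step 2: what the ceiling alone does.** For binomial attendance the variance is 6p(1 − p), so the means fix the spreads.

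*Means 5.4 v 4.8 (p = 0.9, 0.8).* Variances 0.54 and 0.96. Sp² = (39 × 0.54 + 19 × 0.96)/58 = 0.678. Pooled SE = √(0.075 × 0.678) = 0.225. True SE = √(0.54/40 + 0.96/20) = √0.0615 = 0.248. Ratio 0.91.

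*Means 5.7 v 4.8 (p = 0.95, 0.8).* Variances 0.285 and 0.96. Sp² = 0.506. Pooled SE = 0.195. True SE = √0.055125 = 0.235. Ratio 0.83.

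*Means 3.6 v 2.4 (p = 0.6, 0.4).* Both variances are 1.44. Ratio 1.00.

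**Step 3: simulated coverage of a nominal 95% interval (40,000 trials per row).**

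| Measure, PPPA v SPA mean | Model | Pooled | Welch |
|---|---|---|---|
| Sessions 4.8 v 4.8 | binomial | 94.8% | 94.7% |
| Sessions 4.8 v 4.8 | overdispersed | 94.9% | 94.4% |
| Sessions 5.4 v 4.8 | binomial | 92.5% | 94.8% |
| Sessions 5.4 v 4.8 | overdispersed | 92.3% | 94.2% |
| Sessions 5.7 v 4.8 | binomial | 89.4% | 94.7% |
| Sessions 5.7 v 4.8 | overdispersed | 88.5% | 93.5% |
| Sessions 3.6 v 2.4 | overdispersed | 94.8% | 94.7% |
| Sessions 3.0 v 1.8 | overdispersed | 95.5% | 94.7% |
| CSQ-like 27.4 v 27.4 | limited to 8–32 | 95.1% | 95.0% |
| CSQ-like 28.8 v 26.6 | limited to 8–32 | 93.3% | 94.8% |
| CSQ-like 30.0 v 25.7 | limited to 8–32 | 91.1% | 94.9% |

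The shortfall appears only when PPPA is higher and both arms are in the upper range. It is absent when the arms share a distribution, and absent or slightly reversed when attendance is mid-range or lower.

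**The case against.** The strongest reply is that little rides on this. C.5 puts effect sizes ahead of strict significance testing, warns that small samples give large standard errors, and acknowledges the unbalanced sample. H1 is an equal-or-greater hypothesis. In the scenario that causes trouble PPPA really is better, so H1 is true and a slightly narrow interval does not create a wrong conclusion. All of this stands, and it is why the point is minor. It does not remove the point: a pilot that reports effect sizes should report their uncertainty correctly.

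Several stronger readings are tempting, and the documents do not support them.

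- *That the plan expects PPPA to win.* It anticipates equal or higher attendance. If the two distributions are equal, ANOVA is correctly sized: simulated false positives are 5.1 to 5.2% at 4.8 v 4.8.
- *That the H1 tests have an inflated false-positive rate.* That would need equal means with unequal spreads. The ceiling gives unequal spreads only by way of unequal means, and nothing else in the documents suggests that the spreads differ.
- *That the stated error is wrong whichever arm does better.* It is not wrong when the spreads are equal, nor in the mid-range.
- *That the mixed models should also have arm-specific residual variances.* The ceiling argument concerns attendance and the CSQ-8. It says nothing about MVPA, and no check was made for those models.

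One more limit is fair. That ANOVA means the pooled test is an inference from ordinary usage, since the plan does not say so. Nor does Welch deal with clustering within the six treatment groups: at an assumed ICC of 0.05 and 10 per group, the design effect is 1 + 9 × 0.05 = 1.45, which by itself would make the standard error 17% too small (1/√1.45 = 0.83). That is a separate matter.

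**Conclusion.** The point holds conditionally and is minor. For assumed attendance of 5.4 v 4.8 sessions, the pooled standard error is about 9 to 10% too small and coverage is about 92% instead of 95%. It falls to about 88 to 90% only when PPPA is almost at the cap (5.7 of 6). For a CSQ-like score the corresponding range is about 91 to 93%. Welch stays between 93.5 and 95% in all of these cases.

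The conclusion rests on three things: reading ANOVA as the equal-variance test; attendance or satisfaction being high in both arms; and PPPA being higher, which is one of the two outcomes the plan allows for. The documents give neither means nor SDs for these measures, so the sizes are illustrations, not predictions. What would be misstated is the precision of a real difference.

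**What to change.** In C.5, under Feasibility and acceptability, replace analysis of variance for number of sessions attended and CSQ-8 score with the Welch (unequal-variance) comparison, and report its 95% interval. Report the SD of each score by arm, so that a reader can see whether the spreads differed and the next trial can use them. Leave the chi-squared analysis of retention and the mixed models as they are on this account.

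The cost is a wording change in the analysis plan. If the variances turn out equal, the Welch interval is about 1% wider than the pooled one at 40 v 20. No change to design, sample size or data collection is needed.
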